
This is a multicenter, open-label extension (OLE) study of ADS-5102 (amantadine) extended release capsules in subjects with MS and walking impairment who completed study drug treatment for 16 weeks and completed a Week 16 visit in Study ADS-AMT-MS301.
 
Eligibility for inclusion in this study will require all subjects to be willing to abstain from prohibited medications.
 
All enrolled subjects, will receive ADS-5102 at 137 mg for the first week, 205.5 mg for the second week, and 274 mg for the remainder of the 52-week open-label treatment period.
 
Subjects will return to the clinic for safety and efficacy assessments at Weeks 4, 12, 24, and 52. In addition, a telephone visit for safety assessments will be conducted at Week 2 and Week 38. Subjects who withdraw from the study prior to completion of the Week 52 visit will have an early termination (ET) visit that includes safety and efficacy assessments. Subjects who complete 52 weeks of open-label treatment will have a final visit for post-treatment safety follow-up and efficacy assessment at 54 weeks, 2 weeks after their Week 52 visit. The end of study (EOS) is defined as when a subject completes the safety follow-up or ET visit.
	

All study visits and efficacy assessments should be scheduled to occur at approximately the same time of day for each individual subject. Each subject's efficacy assessment should be performed by the same clinical rater, if possible.

Adverse events (AEs) and concomitant medications will be recorded beginning with the first dose of study drug and continuing through the last study visit.

**Number of Subjects (Planned):** Up to approximately 540 subjects will be enrolled.

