## 7. INVESTIGATIONAL PLAN

### 7.1. Overall Study Design

This is a multicenter, open-label study of ADS-5102 (amantadine) extended release capsules in subjects with MS and walking impairment who completed study drug treatment for 16 weeks and completed a Week 16 visit in Study ADS-AMT-MS301.

Eligibility for inclusion in this study will require all subjects to be willing to abstain from prohibited medications.

All enrolled subjects will receive ADS-5102 at 137 mg for the first week, 205.5 mg for the second week, and 274 mg for the remainder of the 52-week open-label treatment period.

Subjects will return to the clinic for safety and efficacy assessments at Weeks 4, 12, 24, and 52. In addition, a telephone visit for safety assessments will be conducted at Week 2 and Week 38. Subjects who withdraw from the study prior to completion of the Week 52 visit will have an early termination (ET) visit that includes safety and efficacy assessments. Subjects who complete 52 weeks of open-label treatment will have a final visit for post-treatment safety follow-up and efficacy assessment at 54 weeks, 2 weeks after their Week 52 visit. The end of study (EOS) is defined as when a subject completes the safety follow-up or ET visit.

All study visits and efficacy assessments should be scheduled to occur at approximately the same time of day for each individual subject. Each subject's efficacy assessment should be performed by the same clinical rater, if possible.

Adverse events (AEs) and concomitant medications will be recorded beginning with the first dose of study drug and continuing through the last study visit.

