### 8.3. Subject Withdrawal Criteria

Subjects will be advised that they are free to withdraw from the study at any time. Reasons that subjects may be withdrawn from the study include the following:

- Subject discontinued study drug (see [Section 8.5](#)) and wishes to withdraw
- Subject consent is withdrawn
- Sponsor decision, after discussion with the investigator

If a subject is withdrawn from the study, all efforts will be made to complete the early termination visit that includes efficacy assessments and safety follow-up. In addition, women of childbearing potential will have a post-study pregnancy test performed at the early termination visit.

All information, including the reason for withdrawal, should be reported on the applicable pages of the case report form (CRF).

For subjects who are lost to follow-up, three documented attempts will be made to contact the subject for follow-up information, including reason for discontinuation and follow-up of AEs.

Subjects who withdraw from the study will not be replaced.

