## **8.5. Discontinuation of Study Drug**

Subjects should discontinue study drug if judged necessary by the investigator or sponsor, and reasons may include any of the following:

- eGFR falls below 60 mL/min/1.73 m^2, confirmed by repeat testing
- Need to take a medication that is excluded or that may interfere with study measurements
  - Subjects requiring MS treatment adjustment due to disease exacerbation or progression should be discussed with one of the Medical Monitors
- Intolerable or unacceptable AEs
- Positive pregnancy test

Subjects who discontinue study drug will be withdrawn from the study, and will have an early termination visit that includes efficacy assessments and safety follow-up (see [Section 12.8](#)).

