## 12. EVALUATIONS BY VISIT

A schedule of study evaluations is provided in [Appendix A](#).

All study visits should occur on the day scheduled  $\pm$  2 days.

### 12.1. Baseline/Week 0

Potential subjects for the study will be fully informed about the nature of the study and possible AEs. Subjects who wish to participate in the study must read and understand the consent form and sign the document after the investigator has answered all questions to the candidate's satisfaction. Further procedures can begin only after the consent form has been signed.

The Week 16 Visit of Study ADS-AMT-MS301 will serve as the Baseline/Week 0 study visit of Study ADS-AMT-MS303 for those subjects who consent to participate. Per the Schedule of Events in [Appendix A](#), procedures that are shared between Study ADS-AMT-MS301 (Week 16 Visit) and the Baseline/Week 0 visit of the present study do not need to be repeated and the data will be captured in both studies.

The following procedures will be performed to establish each subject's qualifications for enrollment into the study:

- The subject is fully informed about the study and gives written informed consent to participate in the study
- Review inclusion/exclusion criteria and evaluate initial subject eligibility
- Record demographic information
- Medical history with an emphasis on the subject's MS and walking impairment, and past treatments for these conditions; alcohol and drug use, other neurological diseases, psychiatric disorders including Major Depressive Disorder or symptom (eg, hallucinations, agitation, paranoia, suicidal ideation), history of seizures, stroke or transient ischemic attack (TIA); history of myocardial infarction (MI) or congestive heart failure (CHF); and history of cancer
- Record all medications currently taken
- Assess and record AEs
- Complete physical examination
- Obtain subject weight in kilograms
- Vital signs (blood pressure, respiratory rate, heart rate, and temperature)
- Blood sample for central laboratory analysis including hematology, serum chemistry, and eGFR
- Urinalysis

- Blood sample for serum pregnancy test in female subjects of childbearing potential
- MSWS-12, T25FW, TUG, and 2MWT assessments (Full details on how individual efficacy assessments are to be performed will be provided in the study manual. These assessments are to be done in this order.)
- Administer the C-SSRS (administration instructions and forms will be provided in the study manual)

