## 12.8. Early Termination Visit

- Assess and record concomitant medications
- Assess and record AEs
- Complete physical examination
- Obtain subject weight in kilograms
- Vital signs (blood pressure, respiratory rate, heart rate, and temperature)
- Blood sample for central laboratory analysis including hematology, serum chemistry, and eGFR
- Urinalysis
- Blood sample for serum pregnancy test in female subjects of childbearing potential
- MSWS-12, T25FW, TUG, and 2MWT assessments (Full details on how individual efficacy assessments are to be performed will be provided in the study manual. These assessments are to be done in this order.)
- C-SSRS
- Collect bottles and evaluate compliance
- Completion of Early Termination Visit CRF, including reason for early discontinuation. (If early termination is due to AE, then a brief narrative of the AE will be recorded in the allocated section of the Early Termination Visit CRF)

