## 12.9. Safety Follow-Up/End of Study Visit

Subjects will return to the clinic 2 weeks after their Week 52 visit (Week 54), ie, after being off treatment for approximately 2 weeks and the following will be performed:

- Assess and record concomitant medications
- Assess and record AEs
- Symptom-directed physical examination, as needed
- Vital signs (blood pressure, respiratory rate, heart rate, and temperature)
- A blood sample for a serum pregnancy test will be collected for females of childbearing potential
- MSWS-12, T25FW, TUG, and 2MWT assessments (Full details on how individual efficacy assessments are to be performed will be provided in the study manual. These assessments are to be done in this order.)
- C-SSRS

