## **13. ADVERSE EVENTS, SERIOUS ADVERSE EVENTS, AND ADVERSE EVENTS OF SPECIAL INTEREST**

During the study, the investigator or study site personnel will be responsible for querying and recording adverse events (AEs) and serious adverse events (SAEs), as detailed in this section of the protocol. In this study AEs and SAEs will be reported from the time of study drug administration until the last study visit or death, or whichever occurs first.

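### Early stoppers end the study at an untimed early termination visit, so any part of the 14-day post-treatment AE period that falls after it has no scheduled contact, and their AE cut-offs conflict

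*Combined protocol and SAP*

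**What the plan says.** Section 8.5 withdraws anyone who stops drug: "Subjects who discontinue study drug will be withdrawn from the study, and will have an early termination visit". It says this visit covers efficacy and safety follow-up and refers to Section 12.8. The Synopsis and Section 7.1 treat that visit as one of two alternative end points: "The end of study (EOS) is defined as when a subject completes the safety follow-up or ET visit".

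Section 12.8 lists one visit's procedures, including an AE check, the C-SSRS and "Completion of Early Termination Visit CRF, including reason for early discontinuation". It gives no day or window and names no later contact. The ET column of Appendix A gives no day either. The general rule in Section 12, "All study visits should occur on the day scheduled" (within 2 days either way), needs a scheduled day, and the ET visit has none.

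Subjects who complete 52 weeks return at Week 54, "ie, after being off treatment for approximately 2 weeks" (Section 12.9).

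The protocol gives three end points for AE or SAE collection:
- The last study visit. Section 7.1 and the Synopsis have AEs "recorded beginning with the first dose of study drug and continuing through the last study visit"; Section 13 has them reported "until the last study visit or death, or whichever occurs first".
- The safety follow-up visit: Section 13.1.2.2 for deaths, the first paragraph of 13.2.1 for AEs, and 13.3.2 for SAEs.
- Fourteen days after treatment stops: the second paragraph of 13.2.1.

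**The concern.** Safety and tolerability is the primary objective (Section 6.1), and intolerable AEs are a listed reason for stopping drug (Section 8.5). The protocol sets its own 14-day post-treatment recording duty. It schedules a contact that meets this duty only for subjects who took drug for the full 52 weeks. For a subject who stops early, nothing after the ET visit prompts the site to ask about new events, however soon after last dose that visit took place.

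The wording adds a second problem. Suppose the ET visit is on day 2 and a new AE starts on day 8. The second paragraph of 13.2.1 requires it to be recorded, while Sections 7.1 and 13 have already closed collection. Sites could reasonably act differently. Whether such an event reaches the TEAE tables in Section 14.6 then depends on chance reporting and on which sentence the site follows, and this applies only to early stoppers.

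**Working it through.** This is calendar arithmetic on the plan's own windows. No power or sample-size figure is involved.

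**Inputs**
- Post-treatment recording period: 14 days (13.2.1, second paragraph).
- Completers' last visit: 2 weeks after the Week 52 visit (12.9), ±2 days (Section 12, Appendix A).
- Last dose for completers: taken as the day of the Week 52 visit, since 9.4 has dosing continue through Week 52 (assumption).
- ET visit day after last dose, d: not given, so left as a variable.

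**Completers (the plan's own figure).** (54 − 52) × 7 = 14 days, or 12 to 16 with the window. Uncovered days run from max(0, 14 − 12) = 2 to max(0, 14 − 16) = 0. The Week 54 visit therefore reproduces the 14-day period to within 2 days.

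**Early stoppers.** Uncovered days = max(0, 14 − d):

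| ET visit on day d | Days of the 14 with no scheduled contact |
|---|---|
| 0 | 14 |
| 3 | 11 |
| 7 | 7 |
| 14 or later | 0 |

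**Cut-offs side by side**

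| Cut-off | Completer | Early stopper |
|---|---|---|
| Last study visit (Synopsis, 7.1, 13) | Week 54 visit, day 12–16 | ET visit, day d |
| Safety follow-up visit (13.1.2.2, 13.2.1 first paragraph, 13.3.2) | Week 54 visit, day 12–16 | Unclear: the ET visit, or a visit they do not have |
| 14 days after stopping (13.2.1 second paragraph) | Day 14 | Day 14 |

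For completers the cut-offs differ by at most 2 days. For early stoppers the first and third differ by |14 − d| days: 12 if the ET visit is on day 2, 7 if on day 7. After day 14 the visit-based cut-off becomes the longer one.

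The middle row cannot be settled from the text. Section 8.5 says the ET visit includes safety follow-up, which points to the ET visit. The end-of-study definition lists the safety follow-up and ET visits as alternatives, which points to a visit early stoppers never have.

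**Number affected.** The protocol gives no expected stopping rate and no ET timing, and the planned 540 is a ceiling. No count follows from the documents, and no AE rate is estimated here.

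**Check of the remedy.** With a call at day 14 to 16, uncovered days are max(0, 14 − 14) = 0 to max(0, 14 − 16) = 0. End of study then never falls before day 14. If the ET visit is itself on day 14 or later, no call is needed and the gap is already 0.

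**The case against.** The strongest reply is that these subjects are not abandoned, and much of it stands.

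- Section 13.1.1 has the investigator follow and treat a subject withdrawn for an AE until it resolves or stabilises, and 13.1.8 extends follow-up to all AEs. Pregnancies are followed to outcome (13.3.3). Two of the four listed reasons for stopping thus already carry follow-up past the ET visit. These duties attach to known events, however, and do not prompt a question about new ones.
- Section 13.3.2 requires notification of related SAEs learned of after discharge. This is passive and limited to related SAEs. New non-serious events, including non-serious hallucinations or suicidality (the two AESIs in 13.1.3), have no equivalent.
- The duty to record AEs for 14 days already exists in 13.2.1. That is true; what is missing is a scheduled contact that would let a site meet it.
- Section 8.3 lists stopping drug and wishing to withdraw as a reason for withdrawal, which suggests that withdrawal might be optional. Section 8.5 is more explicit, and no off-drug visit schedule exists, so the gap remains. The two sections should still be aligned.
- Section 8.3 also provides that "For subjects who are lost to follow-up, three documented attempts will be made to contact the subject". This helps with subjects who disappear, but not with those who attend the ET visit and are then finished.

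A reader might also infer that TEAEs have no end date at all. The documents do not support that: the paragraph of 13.2.1 that defines TEAEs also limits recordable AEs to 14 days after stopping, and Section 14.5 leaves analysis detail to the SAP.

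**Conclusion.** The point holds in a limited form. Early stoppers have max(0, 14 − d) days of the protocol's own post-treatment AE period with no scheduled contact, against 0 to 2 for completers, and their AE and SAE cut-offs conflict. The gap concerns unprompted new events, mainly non-serious AEs and AESIs.

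Three stronger readings are tempting, and the documents do not support them:
- That early stoppers get no safety follow-up. The ET visit includes an AE check and the C-SSRS, and known events are followed afterwards.
- That every early stopper loses the full 14 days. The loss depends on d, and is zero from day 14.
- That the Section 14.6 tables are biased by a calculable amount. Neither the number of early stoppers nor any post-treatment AE rate is available.

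The completer figure assumes that last dose falls on the day of the Week 52 visit. The early-stopper figure rests only on the 14-day period and an unspecified d. This is a worthwhile, inexpensive improvement to ascertainment on the primary objective, and does not threaten the study's validity.

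**What to change.** - Give the ET visit a window in 8.5, 12.8 and Appendix A, for example within 7 days of last dose where possible.
- Add one telephone contact at day 14 (+2 days) after last dose, covering AEs and concomitant medications in the format of the Week 2 and Week 38 calls. The C-SSRS can be optional, since those calls do not include it. The contact applies to early stoppers who have not withdrawn consent or been lost to follow-up, unless the ET visit falls on or after day 14.
- Make that contact their end of study in the Synopsis and 7.1.
- Use one cut-off for AEs, SAEs and deaths, the later of 14 days after last dose and the last study contact, in the Synopsis, 7.1, 13, 13.1.2.2, 13.2.1 and 13.3.2. Keep the 13.3.2 duty on related SAEs learned of later.
- Align 8.3 with 8.5 on whether stopping drug means withdrawal, and name the new contact in 8.3, 8.5, 12.8 and Appendix A.

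The cost is amendment wording and one short call per reachable early stopper. Someone who stops before Week 52 is called at most 16 days later, by about Week 54, so the approximate maximum participation in 7.6 is unchanged. The efficacy analyses are not affected.

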## 9. STUDY DRUG MATERIALS AND MANAGEMENT

### 9.1. Study Drug

The clinical supplies will include open-label 137 mg and 68.5 mg ADS-5102 capsules.

Amantadine is designated generically as amantadine hydrochloride and chemically as 1-adamantanamine hydrochloride. All dose quantities however are based on quantity of amantadine, as per FDA requirements regarding drug products containing salt drug substances.

The clinical formulation is shown in the table below.

**Table 2: Clinical Formulation for Study ADS-AMT-MS303**

Formulation	ADS-5102 137 mg and 68.5 mg Extended release coated pellets of amantadine in an oral capsule
Dose Strength	137 mg amantadine per capsule 68.5 mg amantadine per capsule
Description	White to off-white pellets filled in white opaque/white opaque colored hard gelatin capsule, size 0.
Excipients	Microcrystalline cellulose, NF/EP Hypromellose, USP/EP Copovidone, NF/EP Talc, USP/EP Ethyl cellulose, USP/NF/EP Povidone, USP/EP Medium chain triglycerides, USP/EP/NF Magnesium stearate, USP/NF/EP

USP: United States Pharmacopeia; NF: National Formulary; EP: European Pharmacopoeia.

### 9.2. Study Drug Packaging and Labeling

The study drug will be packaged in child-resistant blister wallets and bottles. Blister wallets will contain 36 capsules to allow for 2 weeks of dosing during the forced titration period (2 capsules per dose, allowing a 2-week supply plus 2 extra doses for each week). Bottles will contain 60 capsules (30-day supply of study drug) of 137 mg ADS-5102. All blister wallets and bottles will be labeled with, at a minimum, the protocol number, route of administration, number of capsules to be administered, lot number, storage conditions, sponsor's name and address, investigator's name, subject number, and applicable investigational drug caution statements.

The study drug will be assigned by an interactive response technology (IRT) system per the assigned dosing schedule and titration scheme at designated study visits. Details of the dispensation schedule will be included in the IRT user manual.

### 9.3. Study Drug Storage

All study drugs must be stored at 25°C (77°F) with excursions permitted to 15-30°C (59-86°F) in a secured location with access limited to authorized personnel.

An authorized pharmacist or designated staff member will dispense the study drug. The dispensing and administration will be recorded in a drug accountability log.

### 9.4. Administration

The dosing regimen is as follows:

- 137 mg/d (1 x 137 mg capsule + 1 placebo capsule) for one week, followed by
- 205.5 mg/d (1 x 137 mg capsule + 1 x 68.5 mg capsule) for 1 week, followed by
- 274 mg/d (2 x 137 mg capsules) for 50 weeks.

Each dose will be administered as 2 oral capsules once daily at Bedtime.

Capsules are to be swallowed intact, and can be taken with any nonalcoholic beverage, with or without food.

While taking study drug, **concomitant use with alcohol is not recommended**, as it may increase the potential for CNS effects such as dizziness, confusion, lightheadedness, and orthostatic hypotension and may result in dose-dumping.

Dosing will continue through Week 52.

### 9.5. Study Drug Accountability

All study drug supplied is for use only in this clinical study and must not be used for any other purpose. The investigator is responsible for the study drug accountability, reconciliation and record maintenance at the investigational site. In accordance with all applicable regulatory requirements, the investigator or designated site staff must maintain study drug accountability records throughout the course of the study. This person will document the amount of study drug received and the amount supplied and/or administered to and returned by subjects, if applicable. Copies of all packing slips for the study drug shipments must be retained.

A Study Drug Accountability Record must be kept current and will contain at a minimum the following information:

- The identification of the subject to whom the drug was dispensed
- The date(s) and quantity of the drug dispensed to the subject
- Any product accidentally or deliberately destroyed
- Current quantity of total study drug supply

Subjects will be instructed to return all used and unused blister cards of study drug for drug accountability purposes. All used and unused blister cards must be saved for reconciliation by the sponsor's study monitor or an assigned designee.

During the study, the study drug and all shipment, accountability and dispensing records must be available for inspection by the study monitor. Drug supply reconciliation is required at the end of the study by the study monitor.

## 9.6. Study Drug Handling and Disposal

After reconciliation, all unused drug supplies will be disposed of according to instructions provided by the sponsor. Records shall be maintained by the investigator of any such disposition of the study drug, which must show the identification and quantity of each unit returned.

## 9.7. Prohibited Medications and Restrictions

The following medications are prohibited during study participation:

- Amantadine, other than provided study drug
- Live attenuated influenza vaccine

Medications that may affect urinary pH, including, but not limited to, carbonic anhydrase inhibitors, sodium bicarbonate, urinary acidification agents, quinine, quinidine, triamterene, or trimethoprim, can affect the elimination of ADS-5102. The excretion rate of amantadine increases rapidly when the urine is acidic, hence, the administration of urine acidifying drugs may increase the elimination of the drug from the body. Alterations of urine pH towards the alkaline condition may lead to an accumulation of the drug, with a possible increase in adverse reactions. Consequently, subjects should be monitored for changes in efficacy or adverse reactions under conditions that alter the urine pH to more acidic or alkaline, respectively.

Products with anticholinergic properties may potentiate the anticholinergic-like side effects of amantadine. Subjects should be monitored for anticholinergic effects. The investigator should consider reducing the dose of anticholinergic drugs, if atropine-like effects appear when these drugs are used concurrently.

While taking study drug, **concomitant use with alcohol is not recommended**, as it may increase the potential for CNS effects such as dizziness, confusion, lightheadedness, and orthostatic hypotension and may result in dose-dumping.

